**CONFIDENTIAL**

Document Date: 29 Nov 2021

Page 20 of 34

ST-AD-008 version 05

## Statistical Analysis Plan

Sponsor Name: Golden Biotechnology Corporation  
Sponsor Protocol ID: GH Covid-2-001

Covance Study ID: 000000203201

### **7.6.2.4 Vital Status, Patients Alive and Free of Respiratory Failure, and COVID-19 Symptoms**

Proportion of patients with vital status of death in both groups on Days 7, 14, and 28 will be summarized compared using the same logistic regression model as the primary model.

Proportion of patients alive and free of respiratory failure on Days 7 and 28 will be summarized and compared using the same analysis as the primary endpoint.

Proportion of patients with each COVID-19 symptoms at baseline and on Days 7, 14, and 28 will be summarized and compared using logistic regression following the same method as the primary endpoint. Shift from baseline in severity table for each COVID-19 symptoms will be provided by treatment group.

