Proportion of patients with vital status of death in both groups on Days 7, 14, and 28 will be compared using logistic regression stratified by the same covariates as the primary model.

Proportion of patients alive and free of respiratory failure on Days 7 and 28 will be compared using the same analysis as the primary endpoint.

COVID-19 symptoms at screening and on Days 7, 14, and 28 will be summarized, and compared using logistic regression following the same method as the primary endpoint.

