#### 7.6.1 Primary Efficacy Analysis

The proportion of patients from each treatment group who are alive and free of respiratory failure on Day 14 will be summarized and compared using logistic regression, with treatment, remdesivir or other authorized treatments for COVID-19 use at baseline (yes vs no) and age at baseline ( $> 65$  years vs  $\leq 65$  years) as covariates. The p-value for treatment effect will be provided based on the Wald test. P-value based on Fisher's exact test will also be provided. Odds ratio along with its 95% confidence interval will be provided based on the exact method. In addition, the risk difference for the treatment effect and 95% confidence interval will be calculated based on the proportion of patients alive and respiratory failure free in the control group and the estimates of odds ratio, along with its 95% confidence interval.

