### **7.6.3 Exploratory Efficacy Analysis**

Subgroup analyses on primary endpoint will be provided for the parameters of age at baseline ( $> 65$  years vs  $\leq 65$  years), sex, and remdesivir or other authorized treatments for COVID-19 use at baseline. The interaction between each mentioned parameter and the treatment effect will be added one at a time into the primary logistic model and the corresponding p-value for that interaction term will be provided.

The impact on efficacy of any new authorized treatments recommended as SoC for COVID-19 during the course of the study will also be evaluated using the same method as above.

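### Death and the subgroup interactions rest on a Wald p-value from the primary logistic model, which carries no information when one arm, or one subgroup-by-arm cell, has no events (minor)

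*SAP*

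**What the plan says.** SAP 7.6.1 fits a logistic regression with treatment, baseline use of authorized COVID-19 treatment and age group. It states that "The p-value for treatment effect will be provided based on the Wald test". For the primary endpoint it adds two safeguards: "P-value based on Fisher's exact test will also be provided" and "Odds ratio along with its 95% confidence interval will be provided based on the exact method".

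SAP 7.6.2.4 uses different wording for its endpoints. Death on Days 7, 14 and 28 is compared "using the same logistic regression model as the primary model". Freedom from respiratory failure on Days 7 and 28 is "compared using the same analysis as the primary endpoint". Read literally, death inherits the model alone, while the respiratory endpoint inherits the whole analysis, including the exact results. Protocol 8.4.2 also names only the regression for death: "compared using logistic regression stratified by the same covariates as the primary model".

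For subgroups, SAP 7.6.3 says that each interaction, on the primary endpoint, is "added one at a time into the primary logistic model and the corresponding p-value for that interaction term will be provided". The type of test for that term is not named; Wald is the natural reading.

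Neither document has a rule for a logistic model in which an arm or cell has no events. SAP 7.6.2.3, by contrast, does prespecify fallbacks for non-convergence of the viral-load model.

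**The concern.** In ordinary logistic regression, if one arm has no events, the likelihood keeps rising as the treatment coefficient goes to minus (or plus) infinity. The standard error grows faster than the coefficient, so the Wald ratio goes to zero and the p-value to 0.5 one-sided (1 two-sided), whatever happened in the other arm. The same occurs for an interaction term when one arm has no failures within one level of the subgroup.

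SAP 7.1 judges results at one-sided 0.025 (significant) and 0.2 (promising trend). In the affected data sets the death test as written could meet neither criterion, even where an exact test would. This applies in both directions, so an excess of deaths on drug against none on placebo would also get an uninformative p-value.

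**Working it through.** **Inputs.** 174 patients randomized 1:1, so 87 per arm (SAP 2.2). Planned rates of the primary endpoint are 78% and 89%, so failures are 22% and 11% (Protocol 8.1). The one-sided criteria are 0.025 and 0.2 (SAP 7.1). The only mortality figure is 21%, from a cited cohort of hospitalized patients (Protocol 8.1). Trial mortality and subgroup shares are not given, so those below are assumptions.

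**The plan's own figure.** The documents state no operating characteristic for the death or interaction tests. The sample size does reproduce: simulating 87 per arm, with futility stops at 20 patients (odds ratio 3.5) and 80 patients (odds ratio 1.2), gives power 0.801 against the stated 80%.

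**Step 1: what the tests return for deaths.** The Wald result is from a Newton-Raphson fit with treatment and two binary covariates, at iteration 20. With no deaths in one arm and k in the other, one-sided Fisher is C(87,k)/C(174,k).

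| Deaths | Wald, one-sided | Fisher, one-sided |
|---|---|---|
| 0 vs 2 | 0.498 | 0.249 |
| 0 vs 3 | 0.498 | 0.123 |
| 0 vs 4 | 0.498 | 0.060 |
| 0 vs 6 | 0.498 | 0.014 |
| 0 vs 10 | 0.498 | 0.0007 |
| 1 vs 8 | 0.021 | 0.017 |

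For 0 vs 6 the coefficient is -18.6 with standard error 4151, so z = -18.6/4151 = -0.0045. For the same data a Firth profile-likelihood test gives 0.006 and a likelihood-ratio test 0.002. The Wald value depends on where the software stops: about 0.25 to 0.29 at iteration 8, 0.44 at 12 and 0.498 from 20. It is never at or below 0.2 from iteration 8 on. The last row shows that one death restores a usable Wald test.

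**Step 2: how often this arises for deaths.** Let p be placebo mortality, with risk halved on drug (assumed), a = (1-p)^87 and b = (1-p/2)^87.

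- Exactly one arm without deaths: a(1-b) + b(1-a). At p = 2%: 0.1725 × 0.5829 + 0.4171 × 0.8275 = 0.446.
- No treated deaths and at least 3 on placebo (3 is the smallest count with Fisher at or below 0.2): b × P(Bin(87, p) ≥ 3).
- No treated deaths and at least 6 on placebo (6 is the smallest count with Fisher at or below 0.025; 5 gives 0.0603 × 83/170 = 0.029): b × P(Bin(87, p) ≥ 6).

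| Placebo mortality | Exactly one arm without deaths | 0 vs ≥3 | 0 vs ≥6 |
|---|---|---|---|
| 1% | 52% | 4% | 0.02% |
| 2% | 45% | 11% | 0.3% |
| 3% | 30% | 13% | 1.3% |
| 5% | 12% | 9% | 3.0% |
| 10% | 1.2% | 1% | 1.0% |
| 21% (cited cohort) | 0.01% | 0.01% | 0.01% |

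With equal mortality in both arms, the first column becomes 49%, 29%, 13%, 2.3% and 0.02% at 1, 2, 3, 5 and 10%, and about 0 at 21%.

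**Step 3: interactions on the primary endpoint.** If the smaller subgroup level holds n patients per arm and the larger m = 87 - n, the chance of at least one empty cell is 1 - (1-0.89^n)(1-0.78^n)(1-0.89^m)(1-0.78^m). For a 20% share, n = 17 and m = 70: 0.89^17 = 0.138 and 0.78^17 = 0.015, the other two terms are negligible, and the result is 15%. Over assumed shares of 10, 15, 20, 25, 30 and 50% it is 42%, 25%, 15%, 8%, 5% and 1%.

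As an example, take failures of 0/17 vs 6/17 in one level and 10/70 vs 13/70 in the other. The two-sided interaction p-value is 0.998 by Wald, 0.032 by Firth profile likelihood and 0.010 by likelihood ratio.

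**The case against.** The strongest reply is that little depends on these p-values. Death counts are summarized by arm in SAP 7.6.2.4, and adverse events leading to death are tabulated under SAP 7.7.2, so 0 against 8 deaths would be seen. Death also counts as failure in the primary composite, which has the Fisher test and exact odds ratio. Vital status is one of several secondary endpoints in a Phase 2 proof-of-concept trial, and the interactions are exploratory. All of this stands, and it sets the severity.

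The sponsor could also say that the exact results in SAP 7.6.1 were always meant for death. The text does not say so, and its contrast with the Day 7 and 28 respiratory endpoint points the other way. An unadjusted Fisher test would not serve the interactions in any case.

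A reader might infer more than the documents support:

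- **That the Wald test loses sight of mortality steadily as the arms separate.** It does not. It breaks at exactly zero and works at 1 vs 8.
- **That subgroup interactions on mortality are at risk.** None is planned; SAP 7.6.3 concerns the primary endpoint, and there the trigger is no failures in one arm within a subgroup level.
- **That a significant mortality difference is likely to be missed.** With risk halved on drug, 0 vs at least 6 deaths has a chance of about 3% at most over the rates shown.
- **That the symptom analyses need a new method.** SAP 7.6.2.4 has them follow the primary endpoint's method, which can be read to include the exact results.

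**Conclusion.** The point holds, and it is minor. As written, the p-value for death, and by implication for the interactions, is uninformative whenever exactly one arm has no deaths or a subgroup-by-arm cell has no failures.

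For deaths the size depends on a rate that the documents do not give. The problem is negligible at the cited 21% and material at about 5% or below. The cited cohort need not represent this trial: Protocol 4.1 and 4.2 restrict entry to WHO scores 3 and 4 and exclude several severe presentations, so a lower rate is plausible, most of all on Day 7. The most relevant loss is a promising trend that the Wald test cannot register (0 treated vs at least 3 placebo deaths), with a chance of 1% to 13% for placebo mortality of 1% to 10% and risk halved on drug.

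For interactions no mortality assumption is needed. At the planned failure rates the chance of an empty cell is 15% or more once the smaller level holds 20% of patients or fewer.

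Two readings are built in: that the logistic model is fitted by ordinary maximum likelihood, and that the interaction p-value is Wald. The primary Day 14 comparison is little exposed at 22% and 11% failures and already has its exact companion.

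**What to change.** In SAP 7.6.2.4, extend the Fisher p-value and the exact odds ratio with its confidence interval to death on Days 7, 14 and 28. State that these are the reported inference when an arm has no deaths, so that it is settled in advance which p-value leads.

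In SAP 7.6.3, base the interaction p-value on a Firth-penalised profile-likelihood test or an ordinary likelihood-ratio test instead of Wald, and name the one chosen.

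For symptoms, only confirm that the method carried over from the primary endpoint includes the exact test.

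The cost is one SAP sentence in each section and, if Firth is chosen, a slight shift in the penalised estimates. The sample size of 174 is unaffected.

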8.3. General Considerations

Continuous variables will be summarized by the standard descriptive statistics: number of patients (n), mean, standard deviation, median, minimum, and maximum. Frequency of patients or events and percentages will be summarized in categorical variables.

Missing values on clinical improvement score will be imputed using Last Observation Carried Forward for a maximum of 1 day at Day 7, 2 days at Day 14, and 4 days at Day 28. For

respiratory failure status, where a patient has died, their status will not be considered missing but will be treated as an observation at each timepoint.

Unless otherwise stated, all regression models will be adjusted for age and remdesivir or other authorized treatments for COVID-19 use at baseline.

Results will be considered statistically significant at one-sided alpha of 0.025, and considered to indicate promising trend at one-sided alpha of 0.2.

Additional information is available in the statistical analysis plan (SAP).

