## Statistical Analysis Plan

Sponsor Name: Golden Biotechnology Corporation  
 Sponsor Protocol ID: GH Covid-2-001

Covance Study ID: 000000203201

Principle	Value
Treatment group labels and order	Antroquinonol 100 mg BID Placebo
Tables	Data in summary tables presented by treatment group, assessment and visit (where applicable).
Listings	All data collected presented by treatment group, country, site, Patient, assessment and visit (where applicable), unless otherwise specified.
Descriptive summary statistics for continuous variables	Number of patients/observations (n), mean, standard deviation (SD), median, minimum (Min) and maximum (Max).
Descriptive summary statistics for categorical variables	Frequency counts and percentages [n (%)]
Denominator and for percentages	Number of patients in the analysis population, unless stated otherwise in table shell(s).
Precision for percentages	1 decimal place
Include "Missing" as category	Yes, when the number missing is greater than zero for at least one treatment group.
Display to one more decimal place than collected value	For efficacy and safety: Mean Mean Difference Median
Display to two more decimal places than collected value	For efficacy and safety: Standard Error Standard Deviation Confidence Interval
Display to three significant figures	For PK: Mean Standard Deviation Geometric Mean Median Min Max
Limit of precision for displays	4 decimal places
Date Format	DDMMYYYY

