#### 7.6.2 Secondary Efficacy Analysis

##### 7.6.2.1 Clinical Improvement Score as Measured by WHO COVID-19 Clinical Improvement Ordinal Scale

Clinical improvement measured as a score on the WHO COVID-19 Clinical Improvement Ordinal Scale will be analyzed using an ordinal logistic regression on Days 7, 14, and 28, with study treatment, clinical improvement score at baseline (as numerical variable), age at baseline ( $> 65$  years vs  $\leq 65$  years), and remdesivir or other authorized treatments for COVID-19 use at baseline (yes vs no) as covariates. The p-value for treatment effect will be provided based on the Wald test.

In addition, descriptive statistics will be provided for average score by treatment group, and the proportion of patients at or below each score, at each visit.

Time to 2-point improvement from baseline in WHO COVID-19 Clinical Improvement score, time to score of 2 or lower, and time to score of 0, will also be analyzed. The hazard ratio and its 95% confidence interval for these time-to-event endpoints will be estimated by Cox proportional hazard model, with treatment, remdesivir or other authorized treatments for COVID-19 use at baseline (yes vs no) and age at baseline ( $> 65$  years vs  $\leq 65$  years) as covariates. The analysis will be carried out using two different censoring rules: 1) Patients will be censored at the time they are provided any authorized treatment for COVID-19 not prescribed at baseline, or on Day 28 if they have not yet recovered or have died by Day 28; 2) Patients will only be censored on Day 28 if they have not yet recovered or have died by Day 28. The p-value for comparison between treatment groups will be obtained based on the Cox proportional hazards model described above. Median time to 2-point improvement, time to score of 2 or lower, and time to score of 0 will be estimated by Kaplan-Meier (KM) method, and the KM curve will be provided.

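### Symptom regressions on Days 7, 14 and 28 omit the same symptom at baseline, costing about 0 to 11 points of power, and symptoms have no stated rule for deaths

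*SAP*

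**What the plan says.** SAP 7.6.2.4 has the "Proportion of patients with each COVID-19 symptoms at baseline and on Days 7, 14, and 28" summarized and "compared using logistic regression following the same method as the primary endpoint". That method, in SAP 7.6.1, is a logistic model "with treatment, remdesivir or other authorized treatments for COVID-19 use at baseline (yes vs no) and age at baseline" group (over 65 or not). Protocol 8.3 sets the same default: unless stated otherwise, "all regression models will be adjusted for age and remdesivir or other authorized treatments for COVID-19 use at baseline". No section adds a baseline symptom term.

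Symptoms are recorded at screening and on Day 1 (Protocol Appendix 5, SAP Appendix 2) and summarized as a baseline characteristic (SAP 7.4). After that they enter one descriptive display: "Shift from baseline in severity table for each COVID-19 symptoms will be provided by treatment group". Elsewhere the SAP does adjust for the baseline value of the outcome. The ordinal model in 7.6.2.1 includes the "clinical improvement score at baseline (as numerical variable"), and the viral load model in 7.6.2.3 includes log viral load at baseline.

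On deaths, the documents give a rule for respiratory failure status (Protocol 8.3), for hospital and ICU days (SAP 7.6.2.2), and for time to improvement and to viral clearance (SAP 7.6.2.1 and 7.6.2.3). Death is score 8 on the ordinal scale (Protocol Appendix 7). For symptoms there is no rule. SAP 6.2 specifies no imputation for them. SAP 7.1 sets the default percentage denominator as "Number of patients in the analysis population, unless stated otherwise in table shell(s"), and the same table adds a Missing category whenever any value is missing.

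**The concern.** Whether a patient has a cough on Day 7 is likely to depend on whether that patient had a cough at entry. If the model leaves that out, a chance difference between the arms at entry partly carries into the later comparison. The test also has less power than the same data could give. The covariate costs nothing to collect, and the SAP already follows this principle for two other secondary endpoints.

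Read literally, the section also tests the arms against each other at baseline. Under randomization any such difference is chance. With seven named symptoms, about 7 × 0.2 = 1.4 would reach the one-sided 0.2 trend level in a given direction with nothing going on. The useful place for the baseline value is inside the later models.

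Without a death rule, the percentages and the odds ratio for the same symptom and visit can describe different sets of patients, and the choice is left to the programmer.

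**Working it through.** **The plan's own figures.** None is stated for symptoms, so the check takes its sample size from the primary endpoint. At 87 per arm with 78% vs 89%, SE(log OR) = √[1/(87·0.78·0.22) + 1/(87·0.89·0.11)] = 0.429. The one-sided 0.2 boundary is exp(−0.842 × 0.429) = 0.697, as Protocol 8.1 states. With both futility rules obeyed, power is 79.9% (binomial simulation) or 81.1% (normal approximation), against the stated 80%. The design figures reproduce.

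**Inputs.** From the documents: 174 patients, 1:1; one-sided 0.025 for significance and 0.2 for a promising trend; the covariates above. Assumed, because the documents give no symptom rates: treatment OR 0.45 within baseline-symptom groups, 40% of placebo patients symptomatic at follow-up, 30–85% symptomatic at baseline, and an odds ratio between baseline and follow-up symptom of 2, 5 or 10. Age group and authorized therapy were in the model with no effect on symptoms.

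**Power, 3,000 simulated trials per row, one-sided 0.025:**

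| Baseline prevalence | Baseline/follow-up OR | Without: log OR (SE) | Power | With: log OR (SE) | Power | Gain (points) |
|---|---|---|---|---|---|---|
| 30% | 2 | −0.799 (0.341) | 66.6% | −0.827 (0.348) | 67.4% | 0.8 |
| 60% | 2 | −0.795 (0.340) | 65.9% | −0.819 (0.347) | 66.2% | 0.3 |
| 85% | 2 | −0.792 (0.341) | 65.0% | −0.803 (0.344) | 65.4% | 0.4 |
| 30% | 5 | −0.696 (0.336) | 54.3% | −0.797 (0.366) | 59.6% | 5.3 |
| 60% | 5 | −0.723 (0.337) | 57.9% | −0.816 (0.360) | 62.0% | 4.1 |
| 85% | 5 | −0.784 (0.340) | 63.6% | −0.813 (0.348) | 65.3% | 1.7 |
| 30% | 10 | −0.624 (0.332) | 47.2% | −0.839 (0.392) | 58.7% | 11.5 |
| 60% | 10 | −0.669 (0.334) | 51.2% | −0.818 (0.374) | 59.6% | 8.4 |
| 85% | 10 | −0.757 (0.339) | 61.5% | −0.814 (0.351) | 63.8% | 2.3 |

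The SE rises with adjustment in every row, but the estimate moves further from zero, so power rises. Check of the largest gain, using power ≈ Φ(|log OR|/SE − 1.96): Φ(1.880 − 1.96) = 46.8% without the term and Φ(2.140 − 1.96) = 57.1% with it. At one-sided 0.2 the same row gives Φ(1.880 − 0.842) = 85.0% and Φ(2.140 − 0.842) = 90.3%, a gain of about 5 points. With no treatment effect and a baseline/follow-up OR of 5, the rejection rate was 2.8% without the term and 2.6% with it.

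A second set of assumptions (60% symptomatic at baseline, 50–60% persistence, 5–10% new onset, treatment OR 0.50–0.55; 1,500 trials each) gave 31.9 to 35.9%, 26.3 to 35.2%, 40.9 to 46.6% and 36.7 to 47.6%, gains of 4 to 11 points. These rates imply a strong association: the baseline/follow-up OR runs from (0.5/0.5)/(0.10/0.90) = 9 to (0.6/0.4)/(0.05/0.95) = 28.5.

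**Chance imbalance.** With those persistence and onset rates, the share of a baseline difference that carries to follow-up is 0.50 − 0.10 = 40% to 0.60 − 0.05 = 55%. At 60% prevalence the between-arm difference at baseline has SD √(2·0.6·0.4/87) = 7.4 points, so a one-SD imbalance moves the follow-up difference by about 3 to 4 points.

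**Deaths.** Assume survivors in both arms have the same symptom prevalence q (20% and 40%), with placebo mortality d and half of that on drug. The 21% row uses the hospital mortality cited in Protocol 8.1. Symptom prevalence is (1−d)q if the dead count as without the symptom, q if they are dropped, and (1−d)q + d if they count as with it. Drug vs placebo odds ratios:

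| Placebo deaths | Counted as without | Dropped | Counted as with |
|---|---|---|---|
| 2% | 1.01–1.02 | 1.00 | 0.95–0.98 |
| 5% | 1.03–1.04 | 1.00 | 0.89–0.94 |
| 10% | 1.07–1.09 | 1.00 | 0.81–0.89 |
| 21% | 1.16–1.21 | 1.00 | 0.68–0.78 |

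At 10% vs 5% deaths and q = 40%, the default percentages would read 0.90 × 40 = 36% and 0.95 × 40 = 38%, while the regression on survivors compares 40% with 40%.

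Dropping the dead is neutral only if survivors are alike. In an extreme case, 40% of each arm would be symptomatic and all deaths (10% vs 5%) fall in that group. Survivors then show 30/90 = 33.3% vs 35/95 = 36.8%, an odds ratio of 0.86 in favor of the arm with more deaths. At 20% symptomatic it is 10/90 vs 15/95, odds ratio 0.67.

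**The case against.** These are secondary endpoints in a proof-of-concept trial. The planned model is prespecified and holds its error rate, and where baseline and follow-up symptoms are only weakly related (OR 2) the covariate gains under 1 point. All of that stands, and it limits the weight of the point. The shift table does use baseline, so baseline symptoms are not ignored by the plan as a whole, but a descriptive table does not correct the test.

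Four stronger readings are tempting, and the documents do not support them.

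- *The dead are counted as symptom-free.* No section says so. With no imputation the regression would ordinarily drop them, and in the tables they would appear as Missing. Only the default denominator keeps them, and the table shells, which are not available here, may override it.
- *A drug with more deaths could pass as better on symptoms unnoticed.* Survivor selection can push that way, as shown above. But deaths are compared in the same SAP section, are failures in the primary endpoint and score 8 on the ordinal scale.
- *The omission loses precision.* For a logistic odds ratio the SE is smaller without the covariate; what is lost is power.
- *The baseline test distorts the later results.* It is uninformative, but it does not enter the Day 7, 14 or 28 models.

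**Conclusion.** The concern holds in a limited form. The Day 7, 14 and 28 symptom models omit an available baseline covariate that the SAP uses in kind for the ordinal score and viral load. The cost is 0.3 to 11.5 points of power at one-sided 0.025, near zero for a weak baseline association and largest for a strong one, and about 5 points at one-sided 0.2 in the most favorable row. Chance baseline imbalance also carries through by 40–55% under the assumed persistence and onset rates. Symptom prevalence, persistence and treatment effect are all assumptions.

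The missing death rule is real but secondary. As written, it leaves survivors in the regression and the whole population in the default percentages. How much that matters depends on mortality by arm, which the documents do not give. The primary analysis is not affected.

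**What to change.** In SAP 7.6.2.4:

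1. Add presence of the same symptom at baseline (yes/no, baseline as defined in SAP 6.1) as a covariate in each Day 7, 14 and 28 model.
2. Replace the between-arm test at baseline with a descriptive summary, and align Protocol 8.4.2, which compares symptoms at screening, or record the departure in SAP Section 8.
3. State that both the regression and the percentages for a visit use patients alive with a symptom assessment at that visit, and show the numbers dead and missing beside them.
4. Add being alive and free of the symptom as a supportive analysis, labeled as mixing mortality into the symptom result. With no symptom effect and deaths of 10% vs 5%, it alone gives an odds ratio of 0.81–0.89 for not being alive and symptom-free. For that reason it should accompany the survivors' analysis and not replace it.

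The cost is SAP wording and table shells. Symptoms at baseline and vital status are already collected. Each model gains one parameter, so the text should also say what is done if a rare symptom prevents convergence.

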### 3.2 Secondary Efficacy Endpoints

- Clinical improvement score as measured by the WHO COVID-19 Clinical Improvement Ordinal Scale, as follows:
  - Time to 2-point improvement from baseline.
  - Supportive analysis, time to score 2 or lower.
  - Supportive analysis, time to score 0.
- Duration of hospitalization (days) up to Day 28
- Virological clearance evaluated using PCR testing from nasopharyngeal or mid-turbinate samples on Day 5, 14, and 28:
  - Time to virological clearance, measured as study days from start of treatment to first negative SARS-CoV-2 PCR test
  - Rate of change in viral load will be evaluated depending on availability of quantitative assays.
- Vital status (death) on Days 7, 14, and 28
- Duration of ICU stay up to Day 28
- Proportion of patients alive and free of respiratory failure on Days 7 and 28
- COVID-19 symptoms on Days 7, 14, and 28. Assessment will evaluate: presence or absence of dry cough, dyspnea (shortness of breath/ difficulty in breathing), or chills/rigors, myalgia (muscle pain), headache, sore throat, and loss of taste or smell; other symptoms that could be related to COVID-19 will also be recorded.

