## 7. Statistical Methods

### 7.1 General Principles

All data processing, summarization and analyses will be performed using Covance's SAS Environment / Version 9.4 (or later) of the SAS® statistical software package.

The following principles will be applied to all TFLs unless otherwise stated:

Principle	Value
Significant tests	Results will be considered statistically significant at one sided alpha of 0.025, and considered to indicate promising trend at one sided alpha of 0.2.

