### 7.4 Baseline Disease Characteristics

Baseline disease characteristics will be listed and summarized by treatment group and overall for the ITT set. Standard descriptive statistics will be presented for the continuous variables of:

- oxygen saturation (SpO2) (%);
- WHO COVID clinical improvement ordinal scale.

The total counts and percentages of patients will be presented for the categorical variables of:

- patient setting;
- chest imaging result (normal, abnormal NCS, abnormal CS);
- SARS-CoV-2 test result (negative, positive);
- WHO COVID clinical improvement ordinal scale (at or below each score);
- COVID-19 symptoms;
- COVID-19 symptoms – maximum severity;
- patients with diarrhea.

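### The SAP tests each COVID-19 symptom between arms before the first dose and exempts none of these tests from the promising-trend rule, so chance imbalances can carry an efficacy label

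*SAP*

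**What the plan says.** - **The comparison.** SAP 7.6.2.4: "Proportion of patients with each COVID-19 symptoms at baseline and on Days 7, 14, and 28 will be summarized and compared using logistic regression". The method is that of the primary endpoint. Protocol 8.4.2, with matching text in the synopsis: "COVID-19 symptoms at screening and on Days 7, 14, and 28 will be summarized, and compared using logistic regression".
- **The method it imports.** SAP 7.6.1 specifies a logistic regression on treatment, COVID-19 therapy at baseline and age group. Its outputs are a Wald p-value, a Fisher p-value, an odds ratio with confidence interval and a risk difference.
- **The endpoint.** SAP 3.2 defines it as "COVID-19 symptoms on Days 7, 14, and 28" and names "dry cough, dyspnea (shortness of breath/ difficulty in breathing), or chills/rigors, myalgia (muscle pain), headache, sore throat, and loss of taste or smell". Other symptoms are recorded as well. Baseline is not among the endpoint days.
- **What baseline means.** SAP 6.1 takes the last value before the first dose. An assessment on the first dosing day with no recorded time is counted as pre-dose.
- **The label.** SAP 7.1: "Results will be considered statistically significant at one sided alpha of 0.025, and considered to indicate promising trend at one sided alpha of 0.2". Its scope is given as "The following principles will be applied to all TFLs unless otherwise stated".
- **The existing baseline table.** SAP 7.4: "Baseline disease characteristics will be listed and summarized by treatment group and overall for the ITT set". COVID-19 symptoms are in its list of categorical variables.
- **Populations.** SAP 7.6 runs efficacy analyses on the ITT, mITT and per-protocol sets, and drops the mITT results if that set is identical to ITT.

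**The concern.** A between-arm test on pre-dose data has nothing to detect. In the ITT set the arms differ at baseline only through the random allocation, so the rejection probability is the test's size whether the drug works, does nothing or harms. A small p-value is a chance imbalance, and a large one does not show that the arms are balanced.

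The text makes this more than a redundant table row. The sentence that calls for the baseline comparison sits in the efficacy section. It imports the full efficacy output, including an odds ratio and risk difference for treatment. It also falls under a labelling rule with a threshold as loose as one-sided 0.2, and nothing exempts the baseline rows. If the plan is followed as written, chance differences at baseline can be reported as promising trends beside the real symptom results.

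**Working it through.** **The plan's own figure.** The documents give no error rate for the symptom tests, so there is none to reproduce on this point. The nearest stated figure is 80% power at one-sided alpha 0.2 with 174 patients (78% versus 89%), for the primary endpoint. Simulating the three looks with the stated futility boundaries gives 80% to 81%, so that figure stands. The symptom tests do not enter it.

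**Inputs from the documents.** Seven named symptoms (SAP 3.2); one-sided alpha of 0.2 for a promising trend and 0.025 for significance (SAP 7.1); 174 patients randomized 1:1, so 87 per arm (SAP 2.2); four compared time points (SAP 7.6.2.4).

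**Assumptions, not in the documents.** The correlation between the seven test statistics; symptom prevalences; and that each Wald test holds its nominal level.

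**Step 1: expected false labels.** Per population, favouring antroquinonol: 7 × 0.2 = 1.4. Correlation does not change this. At one-sided 0.025 it is 7 × 0.025 = 0.175.

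**Step 2: chance of at least one, independent tests.**
- At 0.2, favouring antroquinonol: 1 − 0.8^7 = 79.0%.
- At 0.2, in either direction: 1 − 0.6^7 = 97.2%.
- At 0.025, favouring antroquinonol: 1 − 0.975^7 = 16.2%.

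**Step 3: allowing for correlation.** With equicorrelated normal test statistics at correlation ρ, the chance of at least one is 1 − E[Φ((c − √ρ·X)/√(1 − ρ))^7], where X is standard normal and c is the critical value.

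| ρ (assumed) | one-sided 0.2 | one-sided 0.025 |
|---|---|---|
| 0 | 79.0% | 16.2% |
| 0.1 | 73.9% | 15.5% |
| 0.2 | 69.0% | 14.7% |
| 0.3 | 64.3% | 13.7% |
| 0.5 | 55.1% | 11.5% |

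**Step 4: does the Wald test hold its level?** Simulating the covariate-adjusted model with 174 patients and seven null symptoms gives a per-test rate of 0.20 to 0.21 across the prevalence patterns tried, the lowest being 8%. A latent correlation of 0.5 between symptoms gave test-statistic correlations of 0.22 to 0.32 and at least one label in about 64% to 70% of trials. An exact unadjusted Wald calculation with 87 per arm gives about 19% at 5% or 95% prevalence. It falls to about 14% at 97% and 9% at 2% if tables with an empty cell count as no rejection. Very rare or near-universal symptoms would therefore lower the figures.

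**Step 5: the number of tests.** Seven symptoms at four time points is 28 Wald tests per population. Without baseline it is 7 × 3 = 21.

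**The case against.** The strongest reply is that nothing turns on these tests. The symptom objective and endpoint are confined to Days 7, 14 and 28. Futility uses only the primary endpoint, there is no stopping for efficacy, and the power statement concerns the primary endpoint. A row marked baseline is also unlikely to deceive a careful reader. This stands, and it sets the size of the point. A reader might infer that the trial's proof-of-concept claim is compromised; the documents do not support that.

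A second reply is that the sentence is loosely drafted, with baseline meant for the summary and the shift table only. That is possible, and the table shells are not in the documents, so it cannot be confirmed that baseline p-values would be printed. But both verbs govern all four time points, the protocol has the same construction, and the remedy is the same edit on either reading.

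Third, a stronger statement of the point is tempting in three ways, and each goes too far:
- **That the null is true by design in every population.** This is strict only for ITT. Per-protocol membership depends on later events, including compliance below 50% and prohibited medication (SAP 5.4.1), so selection could produce a baseline imbalance there. First-day assessments without a time are pre-dose only by convention. Neither exception turns a baseline difference into an effect of the drug on symptoms.
- **That 64% to 79% of trials would show a false label.** The lower figure rests on an assumed correlation and is not a floor: at a test-statistic correlation of 0.5 it is 55%.
- **That there are exactly seven p-values per population.** Seven counts only the Wald tests of named symptoms. The primary method adds a Fisher p-value for each, and other recorded symptoms could add more.

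Finally, the SAP 7.4 table covers ITT only, so dropping the test would leave no baseline symptom summary for the other sets unless one is kept.

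**Conclusion.** The point holds, as a minor one. As written, the SAP and protocol compare symptoms between arms before the first dose, outside the endpoint's own definition, and SAP 7.1 attaches its labels to the result. In the ITT set every such label would be a chance finding. About 1.4 false labels favouring antroquinonol are expected if the Wald tests hold their nominal level. The chance of at least one runs from 79% (independent tests) through about 64% (correlation 0.3) to 55% (correlation 0.5). The same figures apply to the mITT and per-protocol sets only if membership of those sets does not depend on arm. The sets overlap heavily, so the figures should not be added across them. The consequence is misleading rows among secondary outputs, and no primary, interim or sample-size decision changes.

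**What to change.** In SAP 7.6.2.4, split the sentence. Baseline symptom proportions are summarized descriptively only, for each analysis set if wanted. The logistic regression, with its p-values, odds ratios and risk differences, applies to Days 7, 14 and 28. Keep the shift-from-baseline severity table, and check that the table shells agree.

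SAP section 8 now reports no changes in statistical methods from the protocol. It should list this as a change from Protocol 8.4.2 and the synopsis, both of which compare at screening.

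The cost is one reworded sentence and one line in section 8. No data or analyses are added, and the seven baseline Wald tests per population, with their Fisher counterparts, disappear. For ITT the descriptive information is already in the SAP 7.4 table.
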